#### 8.4 Statistical Methodology

#### 8.4.1 Data Summary

Descriptive statistics will be computed for all baseline conditions and demographic parameters. That is, for continuous data, the N, mean, median, standard deviation, minimum and maximum will be computed. For categorical data, the frequency will be computed. The data will be presented by appropriate subgroups (e.g., center).

For all additional data collected that are not required for direct support of a study objective, data will be summarized according to visit. For parameters represented by continuous variables (e.g., ROM), the summaries will consist of the N, mean, median, standard deviation, minimum, and maximum values. For categorical variables (e.g., gender), the frequency and percentage in each category will be presented.

For radiographic data, data will be presented according to visits for available parameters. Documentation of statistical analyses will be performed utilizing SAS® software version 9.1.3 or higher.

## 8.4.2 Sample Size Justification

Based on the literature review, it is reasonable to have a reference value of 95% of success rate at five years, and a case success at five years is defined as no incidence of revision and removal of Trident II Acetabular Shell for aseptic loosening within the five-year follow-up period. With the expectation that the success rate of Trident II Acetabular Shell for aseptic loosening within five years will be 94.5%, 277 cases will be needed to have a power of 95% to detect that the 5-year success rate is non-inferior to 95% with a margin of 5% at 5% significance level. After factoring a 20% lost to follow-up rate, a total of 347 cases will be needed.

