# Diagnosis and Main Inclusion/Exclusion Criteria\*

	Required Components:							
	Trident II Tritanium Acetabular Shell:							
	o Clusterhole							
	○ Solidback							
	o Multihole							
	Trident II HA Hemispherical Clusterhole Shell							
	Trident II HA PSL Clusterhole Shell							
	Acetabular components must be used in a cementless							
	application.							
Study Device	If screws are used, only 6.5 mm Low Profile Hex Screws are permissible.							
	The following ancillary devices are permissible:							
	Compatible Stryker Modular Dual Mobility (MDM) acetabular							
	liner							
	Compatible Stryker X3 polyethylene inserts							
	Compatible Stryker femoral bearing heads							
	Compatible Stryker femoral stems							
	Hex Dome Hole Plug							
	Restoration Acetabular Wedge Augments							
Reference Therapy	Literature control, based on cementless acetabular revision.							
	Primary:							
	The 90% confidence interval of the success rate will be computed at							
	five years postoperative. For the non-inferiority comparison, the							
	lower bound of this 90% confidence interval will be compared with							
Statistical	90% survival rate. For the superiority comparison, the lower bound							
Methodology	of this 90% confidence interval will be compared with 95%.							
	Secondary:							
	Radiographic stability will be summarized in table format.							

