#### 8 Statistical Plan

## 8.1 Study Objectives

## 8.1.1 Primary Objective Analysis

The primary hypothesis to be tested will be that the success rate at five years postoperative with the Trident II Acetabular Shell is not worse than 95% with a non-inferiority margin of 5%. That is, the following hypothesis will be tested:

H0: Pt <= 95% - 5% HA: Pt >95 % - 5%

Here, Pt is the success rate at five years postoperative with the Trident II Acetabular Shell. Case success at five years is defined as no incidence of revision and removal of Trident II Acetabular Shell for aseptic loosening within five years.

A 90% two-sided confidence interval will be computed for the success rate at five years. If the lower bound of the confidence interval is greater than a 90% survival rate, then the non-inferiority hypothesis will be supported, that is the five-year success rate is non-inferior to 95% with a margin of 5%. If the lower bound of the confidence interval is greater than 95% then it is supported that the five-year success rate is superior to 95%.

The Kaplan-Meier survival curve of revision and removal of the Trident II Acetabular Shell for aseptic loosening will be displayed using SAS/PROC LIFETEST.

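### 277 evaluable hips do not give the stated 95% power at the 5% level: the planned test has about 87% power, or 91% with a 7% error rate

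*Combined protocol and SAP*

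**What the plan says.** Section 8.4.2 sets the design figures. The reference is justified from the literature: "it is reasonable to have a reference value of 95% of success rate at five years". The planning assumption is slightly lower: "With the expectation that the success rate of Trident II Acetabular Shell for aseptic loosening within five years will be 94.5"%. From these, "277 cases will be needed to have a power of 95% to detect that the 5-year success rate is non-inferior to 95"%, with a 5-point margin and a 5% significance level. Attrition is then added: "After factoring a 20% lost to follow-up rate, a total of 347 cases will be needed".

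Section 8.1.1 puts the null at 95% − 5% = 90% and defines the test through an interval: "A 90% two-sided confidence interval will be computed for the success rate at five years". The rule is: "If the lower bound of the confidence interval is greater than a 90% survival rate, then the non-inferiority hypothesis will be supported". The Statistical Methodology entry of the Study Synopsis repeats this rule. Neither place names the interval method. A Kaplan-Meier curve is mentioned in section 8.1.1, but only as a display.

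Section 8.4.4 bases the primary analysis on the per protocol population, meaning hips available for evaluation at five years. Under the plan's own 20% loss, that is about 277 of 347.

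**The concern.** A 90% two-sided interval whose lower limit must clear 90% is a one-sided 5% test of a 90% success rate. The critical value of such a test is governed by sampling variation at or near 90%, where p(1−p) = 0.0900. At 94.5% it is 0.0520. A sample size that uses the smaller value throughout understates what is needed, and 277 appears to have been obtained that way.

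Two things are at stake. At the sponsor's own expected rate, the risk of missing non-inferiority may be well above the 5% implied by 95% power. And because the interval is not named, an analyst could later choose one that recovers some power by exceeding the declared 5% error rate. This is the study's only powered hypothesis, and section 8.4.3 plans no interim analysis.

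**Working it through.** **Inputs.** Expected success p1 = 0.945, significance level 5%, power 95%, 277 evaluable and 347 enrolled with 20% loss (section 8.4.2). Null p0 = 0.90 and the rule that the lower limit of the two-sided 90% interval must exceed 0.90 (section 8.1.1). Analysis of hips available at five years (section 8.4.4), so the endpoint is treated as a binomial proportion. z(0.95) = 1.645.

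**1. Reproducing the plan's figure.** With the variance at p1 in both terms:

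n = (z + z)² × p1(1 − p1) / (p1 − p0)² = (3.290)² × 0.945 × 0.055 / 0.045² = 277.8

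The plan has 277, for which this approximation gives 94.95% power. Attrition: 277 / 0.80 = 346.25, rounded up to 347. Both figures reproduce. The other variants tried do not give 277: a two-sided 5% level gives 334, the null variance in the type I error term gives 373, and the latter with a continuity correction gives 395.

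**2. Each variance in its own term.**

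n = [z√(p0(1 − p0)) + z√(p1(1 − p1))]² / (p1 − p0)² = [1.645 × 0.300 + 1.645 × 0.228]² / 0.045² = 372.4, so 373

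With n = 277, the same approximation gives 86.9% power.

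**3. The rule applied at n = 277.** For each interval method, find the largest number of failures that still leaves the lower limit above 0.90. Then take exact binomial probabilities at a failure rate of 0.055 (power) and 0.10 (type I error).

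| Lower limit of the 90% interval | Most failures allowed | Power at 94.5% | Type I error at 90% |
|---|---|---|---|
| Clopper-Pearson, Wilson, Jeffreys, log-log, logit | 19 | 86.8% | 4.5% |
| Wald (linear), log, arcsine | 20 | 91.3% | 7.0% |
| None of the methods tried | 21 | 94.5% | 10.4% |

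The third row shows that even a cut-off of 21 failures, which none of these intervals produces, falls just short of 95% power while doubling the error rate.

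**4. What 95% power would require.** With exact limits, 95% power at 94.5% is first reached at n = 379 and is held for every n from 413. (Exact power is saw-toothed in n, hence two figures.) Conversely, with 277 hips and at most 19 failures, 95% power holds only if true success is about 95.2%.

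**5. If all 347 hips contributed.** Were all 347 followed for five years, methods in the first row would give 93.0% power at 4.5% error, and Wald would give 95.4% at 6.7%. A Kaplan-Meier analysis of 347 hips with 20% loss lies between the 277 and 347 cases. Simulation with a constant failure hazard and constant-rate loss (both assumptions, since the plan gives no timing) gives about 89% to 90% power at about 4.5% error with log-log limits. With linear limits it gives about 93% power at about 7% error.

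**The case against.** The strongest reply is that nothing was miscalculated: 277 follows from a recognised large-sample formula, and the gap is between an approximation and exact operating characteristics. That is a fair description of its origin, although the formula is inferred because the plan names none. It does not rescue the statement. Section 8.4.2 claims a power and a level together, and no interval tried delivers both. The Wald interval, which matches the formula, has 91.3% power and misses the level.

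It can also be said that the 7% error rate is conditional, because the plan does not commit to a Wald interval. That is true, and it is presented here only as a condition. But the plan does not exclude it either, and a single permitted failure, 19 or 20, separates 4.5% from 7.0%.

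The 13% risk of failing the test applies at exactly 94.5%. At a true 95%, with 19 failures allowed, it is 6.5%, and at 97% it is under 0.1%. This stands and limits the practical harm, but 94.5% is the rate on which the plan bases its claim.

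Finally, 347 is a minimum and section 2.2.1 sets no maximum per center, so realised power could be higher. That is possible, but it does not make the figure for 277 correct. Lower power does not bias the estimate, and 87% is still respectable. The study is not unsound on this account.

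**Conclusion.** The concern holds. At 277 evaluable hips and a true five-year success rate of 94.5%, the planned test has 86.8% power if the interval holds the 5% level. If a Wald, log or arcsine interval is used, power is 91.3% and the type I error is 7.0%. At the sponsor's expected rate, the risk of missing non-inferiority is therefore about 13% (100 − 86.8 = 13.2), against the stated 5%.

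This rests on treating the endpoint as a binomial proportion in about 277 hips, as the per protocol definition implies. If Kaplan-Meier estimation on all 347 were the primary analysis, power with log-log limits would be about 90% under constant-rate 20% loss. Even complete follow-up of all 347 gives only 93.0% with the level held.

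**What to change.** In section 8.4.2, replace the power statement. With 277 evaluable hips, a true rate of 94.5% and a two-sided 90% interval that holds the 5% level, power is about 87%. State the calculation method (exact binomial) alongside it.

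In section 8.1.1, and in the Synopsis entry that repeats the rule, name the interval: exact (Clopper-Pearson) if the endpoint is analysed as a proportion, or log-log if it is a Kaplan-Meier estimate. State that Wald (linear), log and arcsine limits will not be used for the decision, because at this sample size they allow one more failure and give 7.0% type I error.

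If the primary analysis is changed to Kaplan-Meier on all 347 implanted hips, state about 90% power and the assumed pattern of loss.

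The cost is wording only: the stated power becomes less favourable. Enrolment, endpoint and margin need not change. Keeping the 95% claim would instead require at least 379 evaluable hips with exact limits, or 379 / 0.80 = 473.75, so 474 enrolled at the same 20% loss.

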#### 8.4.3 Interim Analyses

No interim analysis is planned.

#### 8.4.4 Analysis Population

**Per Protocol Population**: The study population for analysis will include all non-censored subjects who received the Trident II Acetabular Shell and are available for efficacy evaluation at the 5-year primary endpoint.

The primary and secondary efficacy analyses will be based on the per protocol population.

**Safety Population**: The safety population will include all non-censored subjects who received the Trident II Acetabular Shell.

The safety analysis will be based on the safety population.

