## 4.3 Early Withdrawal or Termination of Subjects

#### When and How to Withdraw Subjects

In the event that a subject is discontinued by the investigative center prior to the final study evaluation, the subject will be notified by the center that he/she is no longer in the study and a Study Termination eCRF will be completed. If the reason for termination involves the study device not being implanted or surgery not performed, the subject will also be censored from analysis.

The following is a list of reasons for which subjects may be terminated from the study and the date of termination that should be used on the Study Termination eCRF in each situation. This list is not all inclusive:

Termination Reason	Date of Termination
Death	Date of death
Investigative center termination	Date of study close-out visit
Lost to follow-up	Date Stryker termination approval given
Voluntary withdrawal	Date subject notified center of withdrawal
Revision/removal of study device	Date of revision/removal procedure
Study device not implanted	Date of surgery
Surgery not performed	Date Stryker termination approval given

Revision or removal of the Trident II Acetabular Shell for any reason constitutes a failure and a study termination for the subject.

If revision of the femoral head, femoral stem, acetabular insert, or acetabular liner is required during the study, the event does not constitute a failure or study termination.

If the subject fails to return for his/her follow-up appointments, every effort should be made to contact the subject to assess his/her health status. If, after attempting to contact the subject through three documented phone calls and a certified letter, the subject still does not respond, he/she will be considered lost to follow-up. A Study Termination eCRF will be completed only after notifying Stryker of the subject's status and after Stryker has given approval to terminate.

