#### 7.6 Protocol Deviations

Any deviation from this protocol categorized as a 'Major Protocol Deviation' will be recorded by the Sponsor and must be reported to the investigational center's overseeing IRB according to their reporting procedures. Major protocol deviations for this study may include the following; this list may not be all-inclusive:

- Informed consent deviations, including but not limited to:
  - Study procedures performed prior to informed consent
  - Incorrect informed consent version used
- Patient enrolled does not meet the inclusion/exclusion criteria
- Protocol specified study component(s) not implanted
- Off label surgical approach
- Off label component usage
  - If the stem is not a Stryker device it must be revised to a compatible Stryker component or the patient will be censored

If the center anticipates a possible protocol deviation, the investigator or SC should contact Stryker for guidance.

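### The primary set requires availability at 5 years, leaves the place of early-revised hips open and names no estimator; if early failures stay in and independently lost hips drop out, the success rate is biased down

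*Combined protocol and SAP*

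**What the plan says.** Section 8.4.4 defines the primary (per protocol) set as non-censored subjects who received the shell and "are available for efficacy evaluation at the 5-year primary endpoint". The Safety Population in the same section has no such availability condition. Section 8.3 imputes nothing.

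Section 8.1.1 defines case success as "no incidence of revision and removal of Trident II Acetabular Shell for aseptic loosening within five years". Section 4.3 adds: "Revision or removal of the Trident II Acetabular Shell for any reason constitutes a failure and a study termination for the subject". A hip revised for aseptic loosening in year 2 is therefore a failure, and it also leaves the study in year 2.

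On the test, 8.1.1 says: "If the lower bound of the confidence interval is greater than a 90% survival rate, then the non-inferiority hypothesis will be supported". The same limit above 95% supports superiority. The interval is two-sided 90%, but neither its type nor the estimator is named. The only mention of a survival method is: "The Kaplan-Meier survival curve of revision and removal of the Trident II Acetabular Shell for aseptic loosening will be displayed using SAS/PROC LIFETEST".

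Elsewhere, censoring means exclusion. Under 4.3, if the device is not implanted or surgery is not performed, "the subject will also be censored from analysis"; under 7.6, a non-Stryker stem must be revised to a compatible one "or the patient will be censored". So the word non-censored in 8.4.4 does not say how partial follow-up is handled. For a hip lost to follow-up, 4.3 sets the termination date as "Date Stryker termination approval given".

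**The concern.** Two questions are left open: whether a hip terminated by revision belongs to the 5-year set, and which estimator produces the interval.

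On the probable reading, a revision within 5 years settles the outcome, so the hip stays in as a failure, while an event-free hip lost in year 3 has no 5-year status and is dropped. A failure then has to be seen only up to its own date, but a success has to be followed for the full 5 years. Loss removes proportionally more successes than failures, and the rate is pulled down. The sample size allows for fewer hips (277 of 347), not for a shifted rate.

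On the literal reading, a terminated hip is not available at 5 years, and the failures leave the set too.

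The same sentence thus permits either a conservative primary result or one that passes almost by construction.

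**Working it through.** **Inputs from the plan (8.1.1, 8.4.2).** Null 90%, expected success 94.5%, lower limit of a two-sided 90% interval (z = 1.645), stated power 95%, 277 evaluable, 20% loss, 347 total.

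**Assumptions not in the plan.** 20% of hips are lost, independently of loosening and evenly over 5 years. Failures follow a constant hazard, or occur early (Weibull shape 0.5).

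**1. The plan's figure.** n = (1.645 + 1.645)² × 0.945 × 0.055 / 0.045² = 277.8, against 277 stated; 277 / 0.8 = 346.25, so 347. The 95% is a normal approximation with Wald variance. Exactly, with n = 277 and a Wald limit, at most 20 failures pass and power is 91.3%.

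**2. Bias on the probable reading.** Let g be the share of failures that occur before loss.
- Successes seen: 347 × 0.945 × 0.80 = 262.3.
- Constant hazard, g = 0.901: failures seen 347 × 0.055 × 0.901 = 17.2; rate 262.3 / 279.5 = 93.85%.
- Early failures, g = 0.934: failures seen 17.8; rate 262.3 / 280.2 = 93.6%.

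**3. Power, like for like.** The plan's formula is Φ((p − 0.90)/√(p(1 − p)/n) − 1.645).
- Constant: (0.0385 / 0.01437) − 1.645 = 1.03, power 85%.
- Early: (0.0364 / 0.01458) − 1.645 = 0.85, power 80%.

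| | Unbiased n = 277 | Constant hazard | Early failures |
|---|---|---|---|
| Plan's normal formula | 95% | 85% | 80% |
| Actual Wald (exact for unbiased, otherwise simulated) | 91.3% | 81% | 77% |

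The bias costs about 10 to 15 points by either method.

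**4. Sensitivity to timing.** Simulated Wald power, 20% independent loss; late failures are Weibull shape 2:

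| Loss occurs | Constant | Early | Late |
|---|---|---|---|
| In the first year | 89% | 86% | 91% |
| Evenly over 5 years | 81% | 77% | 85% |
| Between years 4 and 5 | 71% | 69% | 73% |

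**5. Kaplan-Meier on all implanted hips** (even, independent loss; constant / early). Mean estimate 94.5%. Log-log limits: power 90% / 91%, type I error 4.3% / 4.4%. Plain limits: type I error 7.1%.

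**6. Loss related to loosening.** Lost hips loosen at 2 or 3 times the rate of followed hips; constant hazard; type I error with log-log limits:

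| | Mean at true 94.5%, 2x / 3x | Type I error, 2x / 3x |
|---|---|---|
| 5-year evaluable set | 94.3% / 94.6% | 3.0% / 5.5% |
| Kaplan-Meier, all hips | 94.9% / 95.2% | 9.5% / 15.3% |

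With early failures the type I errors are 1.4% / 2.3% and 7.2% / 10.3%. The evaluable set is unbiased at about 2.6x (constant) or 5.5x (early); beyond that its bias is upward.

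**7. Literal reading.** About 262 hips remain, with almost no failures. At 262 of 262 the exact lower bound is 0.05^(1/262) = 98.9%, above both 90% and 95%.

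**The case against.** **The plan is not silent on early revisions.** A reader might infer that nothing is said about them. That goes too far: 8.1.1 and 4.3 class an early aseptic revision as a failure, and 8.4.4 with 8.3 in effect drops lost hips of unknown status. What stands is narrower: whether a terminated hip is in the set, and which estimator is tested.

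**The power is not simply 77–81% instead of 95%.** That comparison is tempting but mixes a simulated figure with a normal approximation; about 4 points of the gap (95% against 91.3%) have nothing to do with the analysis set. It also needs even loss and particular failure timings, which the documents do not give.

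**A survival estimate may have been intended.** Section 8.1.1 compares the limit with a survival rate and names PROC LIFETEST, and 8.2.2 plans an all-cause Kaplan-Meier curve. But the text only displays the curve, and the all-cause curve is another endpoint. Applying Kaplan-Meier within the 5-year set would not remove the bias either, because the hips with partial follow-up are already gone.

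**Some lost hips may be recovered.** Contact is yearly to year 10, so a missed 5-year visit need not mean unknown status. This would reduce the effective loss; with 10% loss, Wald power is 90% / 89%.

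**Kaplan-Meier is not uniformly better.** True, as step 6 shows. It is closer to the truth only while lost hips loosen at less than about 1.7x (constant) or 2.7x (early) the rate of followed hips. Moreover, 347 is a minimum, and under independent loss the present error works against the sponsor, not for it.

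**Conclusion.** The concern holds in this form. The primary set is conditioned on 5-year availability, the membership of hips terminated by revision is not stated, and the tested rate has no named estimator or interval.

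If early revisions are kept, lost hips are dropped and loss is independent of loosening, success is underestimated by about 0.6 to 0.9 points (93.9% or 93.6% against 94.5%). Power is about 81% / 77% against 91.3% (actual Wald), or 85% / 80% against 95% (plan's formula). These figures rest on even loss of 20% and the two assumed hazard shapes; other timings give about 69% to 91%.

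A reader might infer that the plan as written invites a false non-inferiority claim. On the probable reading with independent loss it does not: the error is conservative. That protection weakens or reverses if lost hips loosen faster, and no planned analysis would show it. Only the unlikely literal reading makes both tests pass automatically; the wording should rule it out.

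This should be fixed before 5-year data exist. Confidence is high for the gap in the text and lower for any single power figure.

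**What to change.** **8.4.4.** Base the primary analysis on all implanted hips not excluded under 4.3 or 7.6, which is the existing Safety Population. Write *not excluded* in place of *non-censored*.

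**8.1.1.** Take the 5-year success rate and its two-sided 90% interval from the Kaplan-Meier estimate at 60 months, with a named interval such as log-log. Count every shell revision or removal for aseptic loosening up to 60 months as an event. Censor event-free hips at the last date implant status is known, at death, or at removal for another cause. Do not censor lost hips at the sponsor-approval date in 4.3: it falls after last contact, and a 12-month gap would overstate success by about 0.2 points at a true 94.5%.

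**Sensitivity analyses.** (1) The 5-year evaluable set, with earlier aseptic revisions counted as failures. (2) A tipping-point analysis that raises the loosening rate of lost hips after loss until the conclusion changes.

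**8.4.2.** Restate the power for the chosen estimator: about 90% for log-log Kaplan-Meier with 347 hips under even loss. Reaching 95% would take about 420 to 440 hips under the same assumptions.

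**Cost.** Plan wording and a little more analysis. No new data are needed, since the Follow-up Questionnaire already covers survivorship. The real downside is that Kaplan-Meier assumes loss is unrelated to loosening and its type I error rises if that fails, which is why both sensitivity analyses are needed. Censoring deaths and other-cause removals slightly overstates failure (about 0.1 to 0.6 points if 5% to 20% of hips have one), which is conservative.

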## **6 Adverse Events**

## 6.1 Reporting of Adverse Events

The AE reporting requirements for this study are as follows:

- All AEs that meet the definition of serious and occur from intraoperative to 90 days postoperative
- All AEs related to the operative site, regardless of seriousness or time of occurrence

On postoperative functional evaluations, investigators and Study Coordinators (SC) will be prompted to question subjects as to whether they have seen a doctor for any reason, been hospitalized for any reason or have a current impediment to their function.

Additionally, SCs will be responsible for following up with the subjects regarding any questionable responses received on the Follow-up Questionnaire collected in lieu of the completion of a HHS at the 6-week through 10-year intervals. If it is determined upon this further investigation that a protocol-defined AE has occurred, the SC will be responsible for completing an AE eCRF, submitting the event to Stryker and reporting to the IRB as required.

The following decision tree facilitates identification of AEs for which reporting is required under this study protocol:

[figure not shown]

Figure 1. Adverse Event Decision Tree

General Physical Examination Findings

At screening for inclusion into the study, any clinically significant abnormality should be recorded

as a preexisting condition and reported on the Demographics eCRF. From the time of consent

forward, any new clinically significant findings or abnormalities that meet the definition of a

protocol defined AE must also be recorded and documented as an AE.

Adverse Event Reporting Period

The study period during which AEs must be reported is normally defined as the period from the

initiation of any study procedures to the end of the study treatment follow-up. The start of study

procedures is considered to be the point of consent. Any AEs that fit the protocol defined

reportable events must be reported from the time of consent until study completion.

At each contact with the subject, the investigator must seek information on AEs by specific

questioning and, as appropriate, by examination. Information on protocol defined AEs should be

recorded immediately in the source document and also in the appropriate AE module of the eCRF.

All clearly related signs, symptoms and abnormal diagnostic procedure results should be recorded

in the source document and grouped under one diagnosis, as appropriate. The clinical course of

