## 8.2 Safety

## 8.2.1 Safety Parameters

Safety parameters include all protocol-defined adverse events as well as all-cause revision and/or removal of the Trident II Acetabular Shell. For details regarding protocol-defined adverse events, see **Section 6.1**.

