#### 8.2.2 Safety Analyses

The frequency and percentage of all protocol-defined adverse events will be tabulated. All protocol-defined adverse events will be tabulated and 95% confidence interval will be presented. For details regarding protocol-defined adverse events, see **Section 6.1**.

The Kaplan-Meier survival curve of all cause of revision and removal of the Trident II Acetabular Shell at ten years postoperative will be displayed.

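### Read with section 7.6, the safety population in section 8.4.4 leaves out a patient who received the shell but is censored for an unrevised non-Stryker stem (minor)

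*Combined protocol and SAP*

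**What the plan says.** Section 8.4.4 defines two analysis sets. For safety it states: "The safety population will include all non-censored subjects who received the Trident II Acetabular Shell". It bases the safety analysis on that set. The per protocol set, used for efficacy, carries the same non-censored condition and adds availability at the five-year endpoint.

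Section 8.2.1 gives the content of the safety analysis: "Safety parameters include all protocol-defined adverse events as well as all-cause revision and/or removal of the Trident II Acetabular Shell". Section 8.2.2 gives the outputs. On events: "All protocol-defined adverse events will be tabulated and 95% confidence interval will be presented". On revision: "The Kaplan-Meier survival curve of all cause of revision and removal of the Trident II Acetabular Shell at ten years postoperative will be displayed".

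*Censored* has no formal definition. Two places outside section 8.4.4 apply it to a subject:

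- Section 4.3: "If the reason for termination involves the study device not being implanted or surgery not performed, the subject will also be censored from analysis".
- Section 7.6, under off-label component use as a major deviation: "If the stem is not a Stryker device it must be revised to a compatible Stryker component or the patient will be censored".

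Three other places bear on the point:

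- Exclusion G in the synopsis bars a retained non-Stryker stem.
- Section 3.3 confines the analysis to revision cases with an on-label approach. It does not use the word *censored* or say whether safety is meant.
- Section 4.3 lists termination reasons and dates with no entry for the section 7.6 case, and says of that list: "This list is not all inclusive".

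**The concern.** Dropping protocol deviators suits a per protocol efficacy set. A safety set is normally everyone exposed to the device, so that a deviation cannot remove an event from the count. As section 8.4.4 is written, the two sets differ only in the five-year availability requirement, so the deviation filter passes into safety as well.

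At stake is whether the adverse event percentages and the ten-year all-cause curve describe all patients who received the shell. It is also unclear how long a patient censored under section 7.6 would be followed. Section 6.1 says that protocol-defined "reportable events must be reported from the time of consent until study completion", but no passage says whether this patient stays in the study.

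**Working it through.** **Step 1. Whom does the non-censored condition remove?** Setting sections 3.3, 4.3, 7.6 and 8.4.4 side by side:

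| Subject | Received shell? | Rule that applies | In safety set? |
|---|---|---|---|
| No surgery | No | Censored, 4.3 | No; already out without the shell |
| Surgery, shell not implanted | No | Censored, 4.3 | No; already out without the shell |
| Shell implanted, non-Stryker stem not exchanged | Yes | Censored, 7.6 | No |
| Shell implanted, approach not on-label | Yes | 3.3 limits the analysis; *censored* not used | Unclear |
| Any other implanted subject | Yes | None stated | Yes |

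The section 4.3 cases are already excluded by the requirement to have received the shell. Among the stated rules, only section 7.6 gives the non-censored condition any effect on the safety set, and there it removes an exposed patient. No passage puts that patient back.

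**Step 2. The plan's own figures.** The plan gives no count of affected patients and no expected safety rate, so there is none to reproduce. The sample size in section 8.4.2, used below as a denominator, does reproduce:

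- (1.645 + 1.645)² × 0.945 × 0.055 / (0.945 − 0.90)² = 277.8, against 277 stated.
- 277 / (1 − 0.20) = 346.25, rounded up to 347.

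Neither figure depends on the safety definition.

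**Step 3. Illustrative size.** Assumptions, none from the documents except the 347: N = 347 hips implanted, k = 1 to 3 omitted, and a reported crude all-cause revision rate p of 5%, 10% or 20% among the N − k retained. The rate in all implanted hips then lies between

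- p(N − k)/N, if no omitted hip was revised, and
- [p(N − k) + k]/N, if all omitted hips were revised.

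| k | p = 5% | p = 10% | p = 20% |
|---|---|---|---|
| 1 | 4.99–5.27% | 9.97–10.26% | 19.94–20.23% |
| 2 | 4.97–5.55% | 9.94–10.52% | 19.88–20.46% |
| 3 | 4.96–5.82% | 9.91–10.78% | 19.83–20.69% |

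The upward shift is k(1 − p)/N. Its largest value is 3 × 0.95/347 = 0.82 points. The Wald 95% half-width with 344 hips, 1.96 × √[p(1 − p)/344], is 2.30, 3.17 and 4.23 points for the three rates, so the shift stays well inside it. These are crude proportions, not the Kaplan-Meier estimate that section 8.2.2 specifies, and show scale only.

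**Step 4. Rare events.** Suppose the only occurrence of an event falls in one omitted hip. Section 8.2.2 names no interval method, so a two-sided 95% Clopper-Pearson interval is assumed.

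- As reported: 0/346 = 0%, upper limit 1 − 0.025^(1/346) = 1.06%.
- All implanted: 1/347 = 0.29%, interval 0.01% to 1.60%.

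The event disappears from the table.

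**The case against.** **Other readings of the text.** *Censored* could mean time-censoring on a survival curve, and section 7.6 does not repeat the words *from analysis* found in section 4.3. But section 8.4.4 uses the term to decide who belongs to the population, and a time-censored subject is still a member. Sections 8.2.1 and 8.2.2 refer to all protocol-defined events, which points towards inclusion, yet section 8.4.4 decides whose events are counted. That the term is undefined does stand, and is part of the point.

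**It should hardly ever happen.** Exclusion G means only an enrolled deviation can be affected. That stands, and keeps the number small. It does not make the case impossible: section 7.6 writes a specific rule for it, and the Evaluation Schedule places the previous-implant form in the intraoperative column.

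**Nothing is hidden from the sponsor.** Rapid reporting of device-related events, reoperations and revisions (section 6.3), shell retrieval (6.3.2) and product investigation (6.5) are not conditioned on censoring status. This stands. A reader might infer that a safety signal would be lost; the documents do not support that. The gap is in the analysis set, subject to the open question of follow-up.

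**The literature comparison.** A reader might infer that the comparison with published data in section 6.1 would leave out exposed patients. That section speaks of the collected events and does not tie the comparison to the safety population. It is affected only if it is made from that population.

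**Conclusion.** The point holds as a minor one. Following the plan as written, an implanted patient censored under section 7.6 is left out of the section 8.2.2 tables and the ten-year all-cause curve. This rests on reading *censored* as removed from analysis, as section 4.3 does. Whether cases without an on-label approach are also left out of safety is unclear; the documents do not establish that they are.

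The number affected is not stated and the true effect cannot be calculated. The 0.82-point ceiling holds only under the assumed 1 to 3 omissions and 5% to 20% rates, and requires every omitted hip to be revised. The safety outputs are descriptive, with no threshold that depends on them.

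Two further inferences should be resisted. One is that the omission favours the device: the direction depends on whether the omitted patients do better or worse than the rest, which nothing in the documents settles. The other is that the primary analysis escapes because it uses the per protocol set: that set carries the same non-censored condition, so section 7.6 removes the patient there too. What is true is narrower: redefining the safety population leaves the primary analysis as written.

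**What to change.** - In section 8.4.4, define the safety population as all subjects in whom a Trident II shell was implanted, regardless of protocol deviation.
- Define *censored*. Confine the section 7.6 exclusion, and the section 3.3 exclusion so far as it bears on safety, to the per protocol efficacy set. Subjects without surgery or without the shell stay out of all analyses, as section 4.3 has it.
- Reconcile sections 3.3, 4.3, 7.6 and 8.4.4, and state whether a patient censored under section 7.6 stays in follow-up. If not, tabulate events up to the date of leaving and time-censor the patient on the all-cause curve at that date.
- Report the number of implanted subjects excluded from the per protocol set, with reasons.

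The change concerns analysis definitions only and takes no view on the stem rule itself. It costs protocol and SAP wording and probably a few more cases to tabulate. Follow-up will be truncated for any such patient who leaves the study, and safety rates may come out slightly less favourable.
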